6.3.14. End of Study

An EOS visit will be required for all subjects 4 weeks following their last dose of study drug. Subjects who complete an Early Study Drug Discontinuation visit during Induction or ATE will also be required to return for an EOS visit.

Subjects should be instructed to fast from food and non-clear fluids on the evening prior to the EOS visit to ensure a minimum 8-hour fast prior to the fasted blood sample collection.

The following procedures will be performed at the EOS visit:

- Vital signs
 - Heart rate (HR) and systolic and diastolic blood pressure (BP)
 - Respiratory rate
 - Body Temperature
- 12-lead ECG
- Physical examination is to be conducted according to local practice
- Fistula drainage assessment (if applicable) to determine the number of fistula and confirm draining is occurring.
- Weight
- Blood collection
 - Hematology
 - Serum chemistry
 - Overnight fasting lipid panel
 - [REDACTED]
 - [REDACTED]
- Urine collections
 - Urinalysis
 - Pregnancy test for females of childbearing potential – If urine b-hCG test is positive, confirmation with serum b-hCG test is required

- Disease Assessments
 - CDAI Components
 - Abdominal Pain and Total Stool Frequency Scores
- Review concomitant medications
- Adverse event assessment (AEs, SAEs, Adverse Events of Special Interest)
- Review diary completion and compliance and collect diary from subject

6.3.15. Early Study Drug Discontinuation

Subjects who prematurely discontinue the study drug due to adverse events (AEs), lack of response, or any other reason besides withdrawal of consent during Induction or ATE will be asked to return for an Early Study Drug Discontinuation visit. This visit will be conducted within 5 days after the last dose of study drug, if possible. Subjects will also return for the EOS visit for collection of safety data and assessment of disease activity.

During ATE, subjects should be assessed for clinical benefit and if there is no clinical benefit, as deemed by the investigator, the subject should stop study drug treatment and be withdrawn from the study.

Subjects should be instructed to fast from food and non-clear fluids on the evening prior to the Early Study Drug Discontinuation visit to ensure a minimum 8-hour fast prior to the fasted blood sample collection.

The following procedures will be performed at the Early Study Drug Discontinuation visit:

- Tobacco use status
- Vital signs
 - Heart rate (HR) and systolic and diastolic blood pressure (BP)
 - Respiratory rate
 - Body Temperature
- 12-lead ECG
- Physical examination to be conducted according to local practice
- Fistula drainage assessment (if applicable) to determine the number of fistula and confirm draining is occurring.
- Weight
- Blood collection
 - Hematology
 - Serum chemistry
 - Overnight fasting lipid panel
 - [REDACTED]

- [REDACTED]
- Urine collection
 - Urinalysis
 - Pregnancy test for females of childbearing potential – If urine b-hCG test is positive, confirmation with serum b-hCG test is required
 - Fecal collection [may be collected within 3 full days (approximately 72 hours) prior to the visit; however, it is preferable that the stool sample be collected during the first bowel movement in the morning]
 - [REDACTED]
 - Disease Assessments
 - CDAI Components
 - Abdominal Pain and Total Stool Frequency Scores
 - [REDACTED]
 - [REDACTED]
 - Perform drug accountability and review subject's compliance with study drug dosing
 - Review concomitant medications
 - Adverse event assessment (AEs, SAEs, Adverse Events of Special Interest)
 - Review diary completion and compliance; counsel subject as needed Description of Study Assessments

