The randomization will be stratified by prior biologics failure (as defined in [Appendix 4](#)) and CDAI score category (≤ 300 , > 300) at the Screening Stage 2 visit. Approximately 40-60% of subjects randomized will have failed prior treatment with biologics. There will be a cap for enrollment of subjects once one of the biologics stratum reaches 60%. There will also be a cap at 10% for enrollment of subjects with an SES-CD score at screening in the range of 3 to 5. Subjects will be treated for 12 weeks and assessed for the various endpoints, including those that incorporate findings from an ileocolonoscopy and biopsies at the Week 12 visit. Corticosteroids will start to be tapered at Week 8 with the tapering regimen described in [Section 6.4.30](#).

Subjects will undergo clinic study visits every 4 weeks in accordance with [Table 1](#). During this time, subjects will continue to fill out a daily diary.

ATE:

All subjects who complete Induction at the Week 12 visit will continue into ATE, where subjects will be treated with either 80 mg or 200 mg of TD-1473 for 48 weeks. Dose during ATE depends on treatment assignment during Induction ([Figure 1](#) and [Table 2](#)); those who were dosed with TD-1473 during Induction stay on the same dose; those who were dosed with placebo during Induction will be dosed with TD-1473 at 80 mg.

Table 2: Induction and Active Treatment Dose Assignment

Induction Dose (3:3:2 randomization)	Active Treatment Extension (ATE) Dose
80 mg	80 mg
200 mg	200 mg
Placebo	80 mg

During ATE, subjects will undergo clinic study visits every 4-12 weeks in accordance with [Table 1](#). Subjects will continue to complete a daily diary.

Corticosteroids will continue to be tapered during ATE with the tapering regimen recommended in Section 6.4.30. Subjects who have not shown clinical improvement (as assessed by the investigator) 16 weeks after initiation of ATE (i.e., ATE Week 16) should be discontinued from the study following completion of an End of Study (EOS) visit.

End of Study (EOS) Visit:

[figure not shown]
An EOS visit will be required for all subjects 4 weeks following their last dose of study drug. Subjects who complete an Early Study Drug Discontinuation visit during Induction or ATE will also be required to return for an EOS visit. Subjects will continue to complete a daily diary through the last day of the study participation.

Early Study Drug Discontinuation:

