6. STUDY PROCEDURES

Study procedures will be performed only after written informed consent is obtained. The Screening visits (i.e., Stage 1 and Stage 2) will be performed within 35 days before dosing. One repeat Screening Stage 1 visit is allowed for each subject per the investigator's discretion. No more than one repeat Screening Stage 1 visit or repeat visit-specific procedure/assessment is allowed for each subject, unless prior written approval has been provided by the Sponsor. If the subject does not begin Induction treatment within this 35-day window, Screening evaluation procedures (i.e., Stage 1 and Stage 2) must be repeated. Subjects may be considered for re-screening of both Screening Stage 1 and Screening Stage 2 procedures, depending on the reason for the initial screening failure, per consultation with and approval from the Sponsor.

During the study, every effort should be made to perform study procedures as listed in the Schedule of Study Procedures (Table 1). Assessments will be made and biological samples will be taken in the following recommended order at those study visits at which they coincide: fecal sample collection, adverse event assessment, ECG, vital signs, [REDACTED] clinical laboratory safety samples, [REDACTED] and ileocolonoscopy with biopsies (although ileocolonoscopy should be done within 3 days prior to the Week 12 clinic visit). Study drug administration will be in-clinic on Day 1, Week 4, Week 8, Week 12, ATE Week 16, ATE Week 24, ATE Week 36, and ATE Week 48 after all pre-dose assessments [REDACTED] and procedures have been completed.

Throughout the study, the acceptable window for scheduled assessments is as follows:

- - 3 to + 5 days from the nominal visit date for Week 4, Week 8, ATE Week 4, ATE Week 8, ATE Week 16, ATE Week 24, ATE Week 36, ATE Week 48 and the EOS visits
- -1 to +3 days from the nominal Week 12 clinic visit for the Week 12 ileocolonoscopy with biopsies. The Week 12 ileocolonoscopy and biopsies should be performed on the same day as the Week 12 visit, preferably in the early morning, to permit morning dosing with study drug. However, if not feasible to perform both the ileocolonoscopy and the clinic visit on the same day, the ileocolonoscopy could be performed within 3 days after the Week 12 clinic visit. However, the Week 12 endoscopy must be performed at least 1 day prior to ATE Day 1.
- + 3 days from the nominal visit date for the Week 12 clinic visit

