1.4. Schedule of Assessments

The schedule of assessments is presented in Schedule of Assessments

Dispense Electronic Diary ^J	X															
Corticosteroid Dosing Taper (if applicable) ^K				X		X	X	X								
Telephone Call ^L					X											
Concomitant Medications	-----X-----															
Adverse Event Assessment ^M	-----X-----															
Laboratory Assessments																
Pregnancy Test (females of childbearing potential only) ^N	X		X	X	X		X	X	X	X	X	X	X	X	X	X
FSH ^O	X															
Chemistry, Hematology	X		X	X	X		X		X	X	X	X	X	X	X	X
Urinalysis	X		X	X	X		X		X	X	X	X	X	X	X	X
Overnight Fasting Lipid Panel		X ^P	X	X	X		X		X	X	X	X	X	X	X	X
Viral hepatitis and HIV Serology Panel	X ^Q															
██████████ ██████████		■ ^R	■	■	■		■		■	■	■	■	■	■	■	■
Tuberculosis Test (QuantiFeron)	X															
Ileocolonoscopy and Biopsies		X ^R					X ^C									
Fecal Sample for Infectious Studies ^S	X															
██████████ ██████████ ██████████			■ ^R				■ ^R				■ ^R		■ ^R		■ ^R	

██████████ ██████████			■	■	■		■	■	■	■		■				
██████████ ██████████ ██████████		■	■	■	■		■	■	■	■		■		■	■	■
Genetic Blood Sample (Optional – only collected for subjects who provide genetic testing consent)			X													
Disease Assessments																
CDAI Score		X ^v	X	X	X		X		X		X	X		X	X	X ^A
██████████ ██████████		■	■	■	■		■		■	■	■	■		■	■	■
SES-CD Score		X					X									
Fistula Drainage Status (yes/no to active drainage), if fistula is present	X		X	X	X		X					X		X	X	X
██████████			■				■				■	■		■	■	
██████████			■				■				■	■		■	■	
Subject Diary Completion and Compliance Review ^J	X	X	X ^w	X	X		X	X	X	X	X	X	X	X	X	X ^A

Abbreviations: ECG, electrocardiogram; FSH, follicle stimulating hormone; ██████████; ██████████; ██████████; CDAI, Crohn’s Disease Activity Index; SES-CD, Simplified Endoscopy Score; ██████████; EOS, End-of Study, ATE, Active Treatment Extension

A. This visit is for subjects who prematurely discontinue the study drug. This visit will be conducted within 5 days of the last dose of study drug, if possible. Subject will also return for the EOS visit for collection of safety data and assessment of disease activity. Subjects who discontinue study drug early due to AE are permitted to optionally complete their daily diary through to the EOS visit. Subjects who have not shown clinical improvement at ATE Week 16 should complete an Early Study Drug Discontinuation visit and be discontinued from study drug.

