3.1.3. Visit Windows

All assessments will be summarized using analysis windows.

The terminology of unscheduled will be applied to assessments that are outside an analysis window regardless of the nominal label associated with the assessments in the EDC system.

The following visit windows will be used in the summary of clinical data.

Table 6: Visit Analysis Windows

Nominal Visit	Nominal Day	Start (days)	Stop (days)
Screening	NA	-28	-1
Baseline	1	1	Induction Day 1
Week 4	Induction Day 28	Induction Day 21	Induction Day 35
Week 8	Induction Day 56	Induction Day 49	Induction Day 63
Week 12	Induction Day 84	Induction Day 77	Earliest of: 
 • ATE Day 1 dose date • Induction Day 98 (Induction Day 112 for SES-CD score)
ATE Week 4	ATE Day 28	ATE Day 21	ATE Day 35
ATE Week 8	ATE Day 56	ATE Day 49	ATE Day 63
ATE Week 16	ATE Day 112	ATE Day 105	ATE Day 126
ATE Week 24	ATE Day 168	ATE Day 161	ATE Day 182
ATE Week 36	ATE Day 252	ATE Day 245	ATE Day 266
ATE Week 48	ATE Day 336	ATE Day 329	ATE Day 350

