3.3.4. Primary Efficacy Analyses

3.3.4.1. Primary Estimand

The primary estimand uses a treatment policy strategy that considers the efficacy response in subjects regardless of use of rescue medication.

Population:

Subjects with moderately-to-severely active CD [as defined by a CDAI score of 220-450 and SES-CD score of ≥ 6 (≥ 4 if isolated ileal disease) with ulceration (corresponding to a score of 1) in at least 1 of the 5 ileocolonic segments on the Presence of Ulcers subscore of the SES-CD] who are corticosteroid-dependent or have demonstrated inadequate response or intolerance to conventional therapy (aminosalicylates, corticosteroids and immunomodulators such as azathioprine, 6-mercaptopurine, or methotrexate) or biologics (e.g., anti-TNF therapy, anti-IL-12/23, anti-integrin). A subset of subjects (up to approximately 10%) will have an SES-CD score between 3 and 5 points, inclusive.

Variable:

Change from baseline in CDAI score at Week 12. Subjects with any of the following intercurrent events (ICE) prior to Week 12 will have data analyzed as collected following ICE under Treatment Policy approach.

Intercurrent events:

The following are the intercurrent events considered for this study:

Treatment Failure ICE:

1. Prohibited medication for AE of worsening CD (Section 5.7)
2. Any gastrointestinal resection
3. Increase in dose of oral corticosteroids for CD above baseline dose

4. Initiation of oral corticosteroids or aminosalicylates for CD where they were not ongoing at baseline
5. Discontinued study intervention due to AE of worsening CD or lack of clinical benefit

Other ICE:

6. Discontinued study intervention due to COVID-19
7. Discontinued study intervention for reasons other than COVID-19, AE of worsening CD or lack of clinical benefit
8. No attempt to taper steroids from Week 8

Population-level summary:

The mean difference in change from baseline CDAI score at Week 12 between each TD-1473 group and placebo.

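### The primary estimand is treatment policy for stopping study drug, but no Week 12 CDAI is scheduled after an Induction stop, so early stoppers' Week 12 result rests on a missing-at-random assumption

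*Protocol*

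**What the plan says.** SAP 3.3.4.1 defines the primary estimand as the Week 12 change in CDAI under a treatment policy strategy. Its intercurrent events (ICEs) include stopping study drug for worsening Crohn's disease or lack of benefit (ICE 5), for COVID-19 (ICE 6) and for any other reason (ICE 7). Subjects with any listed event before Week 12 "will have data analyzed as collected following ICE under Treatment Policy approach".

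After an Induction stop, Protocol 3.1 and 6.3.15 ask for an Early Study Drug Discontinuation visit within 5 days of the last dose. Protocol 6.3.15 adds: "Subjects will also return for the EOS visit for collection of safety data and assessment of disease activity". CDAI components are collected at both visits. Protocol 6.3.14 sets the timing: "An EOS visit will be required for all subjects 4 weeks following their last dose of study drug". Protocol 3.1, under Early Study Drug Discontinuation, instead counts the 4 weeks from the discontinuation visit. Neither section keeps these subjects on the Week 12 schedule.

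The diary rules differ too. Protocol 3.1 says "Subjects will continue to complete a daily diary through the last day of the study participation", and schedule footnote J also runs the diary to EOS. Footnote A in SAP 1.4 says "Subjects who discontinue study drug early due to AE are permitted to optionally complete their daily diary through to the EOS visit".

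SAP 3.1.5.1 limits induction analyses to data up to the earlier of the ATE Day 1 dose and 5 days after the last dose. SAP 3.3.4.3 treats missing values as MAR within the repeated measures model of Weeks 4, 8 and 12.

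**The concern.** A treatment policy estimand for drug discontinuation needs outcomes measured after discontinuation, at the time point of interest. The plan names the strategy but does not schedule the measurement. Where no Week 12 value exists, the model infers one from the subject's earlier values and from other subjects, most of whom stay on drug. For those subjects the result moves towards what would have happened without the stop, while the label still says treatment policy.

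This matters most if stopping differs by arm, for example adverse-event stops on active drug and lack-of-benefit stops on placebo. Protocol 6.5.1 and 7.1.4 direct discontinuation for most adverse events of special interest, so such stops are foreseeable. SAP 3.1.5.1, read literally, would also remove the off-drug CDAI values that the EOS visit does collect.

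**Working it through.** **Inputs**
- Week 12 is nominal Day 84. The clinic visit is allowed up to "3 days from the nominal visit date for the Week 12 clinic visit" (Protocol 6). The CDAI analysis window opens at "Induction Day 77" and closes at Day 98 or the ATE Day 1 dose if earlier (SAP 3.1.3).
- Whether a record falls in a window is judged "regardless of the nominal label associated with the assessments in the EDC system" (SAP 3.1.3), so an EOS CDAI on Day 77-98 can count as Week 12.
- With D as last-dose day, the discontinuation visit is at D to D+5.
- EOS is at D+28 (Protocol 6.3.14) or at D+28 to D+33 (Protocol 3.1), with a visit window of -3 to +5 days (Protocol 6).
- Planned effects are 45 and 60 points, SD 100, allocation 60/60/40 (Protocol 8.2).
- No discontinuation rate is assumed. A 10% figure appears only as a trigger for replacing subjects (Protocol 6.5.2).

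**The plan's own figure.** Simulating the Hochberg test on these inputs gives 80.8% power for at least one dose and 56.1% for both with known SD (80.1% and 55.5% with pooled-SD t-tests). The plan states 82% and 58%. The agreement is close and has no bearing on this point. The plan gives no discontinuation cut-off to reproduce.

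**1. Lower gap, from visit timing alone**
- Nominal EOS: D+28 ≥ 77 gives D ≥ 49.
- EOS 5 days late: D+33 ≥ 77 gives D ≥ 44. EOS 3 days early: D+25 ≥ 77 gives D ≥ 52.
- Protocol 3.1 timing at its latest (discontinuation visit at D+5, EOS 28 days later, 5 days late): D+38 ≥ 77 gives D ≥ 39.

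The first last-dose day with a Week 12 CDAI is therefore nominally 49, with a range of 39 to 52.

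**2. Upper gap**
- Nominal EOS: D+28 ≤ 98 gives D ≤ 70. For D = 71-76 it falls on Day 99-104, outside the window.
- The discontinuation visit reaches Day 77 only if D+5 ≥ 77, so D ≥ 72, and only if held late.
- An early EOS (D+25 ≤ 98) rescues D ≤ 73. Some of those with D = 71-76 therefore have no Week 12 value.

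**3. With SAP 3.1.5.1 applied**
- Usable data end at D+5. D+5 ≥ 77 gives D ≥ 72. Nobody stopping before Day 72 has a usable Week 12 CDAI, whatever the EOS visit collected.

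**4. What still reaches the model**
- Without the SAP 3.1.5.1 limit, nominal EOS falls in the Week 8 window (Day 49-63) for D = 21-35 and in the Week 4 window (Day 21-35) for D = 1-7. That is 15 + 7 = 22 of the 48 last-dose days before Day 49.
- For D = 8-15 the discontinuation visit is at Day 20 or before and nominal EOS is at Day 36-43. Neither lies in a model window.

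**5. Planned analyses against this gap**
- Sensitivity Analysis 1 (SAP 3.3.5.1) is an ANCOVA assuming missing completely at random. That is a stronger assumption than MAR, so it does not test departures from MAR. Protocol 8.5.2 promised an assessment of MAR and listed this ANCOVA separately.
- Supplementary Estimand 1 (SAP 3.3.6.1) sets change to zero after ICE 5, but sets data after ICE 6 and 7 to missing under MAR.
- Supplementary Estimand 2 (SAP 3.3.6.2) restricts to subjects who reach Week 12.

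**6. Illustration (assumed: 10-20% stop, evenly over Days 1-83; active-arm stoppers lose all benefit; the model credits them with full benefit; placebo mean unaffected)**
- Share before Day 49: 48/83 = 0.578. Subjects: 160 × 0.10 × 0.578 = 9.3, to 160 × 0.20 × 0.578 = 18.5.
- Overstatement of a 60-point effect: 60 × 0.10 × 0.578 = 3.5, to 60 × 0.20 × 0.578 = 6.9 points.
- With the Day 72 cut-off: 71/83 = 0.855, giving 60 × 0.10 × 0.855 = 5.1, to 60 × 0.20 × 0.855 = 10.3 points.
- SE of a dose-placebo difference: 100 × √(1/60 + 1/40) = 20.4. So 3.5-6.9 points is 0.17-0.34 SE, and 5.1-10.3 points is 0.25-0.50 SE.

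**The case against.** The strongest reply is that the plan still produces a Week 12 estimate and that part of the gap is covered. Several stoppers supply off-drug Week 4 or Week 8 values that inform the model (step 4). Supplementary Estimand 1 gives stops for worsening disease or lack of benefit a zero change and is plotted beside the primary result (SAP 3.3.4.2). SAP 3.3.6.6 tabulates Week 12 completeness and ICEs. Subjects with other ICEs who stay on drug, such as a steroid increase, do have Week 12 data. The illustrated bias is well below one standard error. The SAP also records early termination (SAP 1), so a protocol amendment may no longer be practical.

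Most of this stands and limits the point. It does not remove it. Stops under ICE 6 and 7, which include adverse events other than worsening disease, rest on MAR in both the primary analysis and Supplementary Estimand 1. The off-drug Week 4 and Week 8 values from EOS visits survive only if SAP 3.1.5.1 does not apply.

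A reader might infer from the optional diary that the EOS CDAI cannot be computed after an adverse-event stop. SAP 3.3.2 does not support that. Extra-intestinal manifestations, abdominal mass, haematocrit and weight make four subscores, which is the minimum, and missing subscores are carried forward. The score would exist, but its stool, pain and well-being parts could predate the visit. The diary rule affects data quality and needs reconciling; visit timing creates the gap.

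**Conclusion.** The point holds in a limited form. The stated strategy for drug discontinuation is treatment policy, but Week 12 CDAI is not scheduled after an Induction stop. Subjects with a last dose before about Day 49 (nominal; Day 39-52), and some on about Day 71-76, have no observed value. If SAP 3.1.5.1 governs the primary analysis, everyone stopping before about Day 72 is affected, and that section contradicts SAP 3.3.4.1. For these subjects the result rests on an assumption that the planned analyses do not adequately test.

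A reader might go further and conclude that the Week 12 treatment policy question cannot be answered for early stoppers. That is too strong: the repeated measures model gives an answer, but under MAR rather than from observed off-drug data at Week 12.

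Nor is 3.5-7 points an estimate of the bias. It is the most that the stated scenario gives for a 60-point effect on the Day 49 cut-off. The documents give no discontinuation rate, and departures in the placebo arm could move the difference either way. The true size is unknown.

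**What to change.** 1. **Follow-up.** In Protocol 3.1 and 6.3.15 and schedule footnote A, have subjects who stop drug in Induction without withdrawing consent provide the diary and the CDAI components at the scheduled Week 12 date, without ileocolonoscopy. Reconcile the diary rule (footnote A against Protocol 3.1 and footnote J) and the two EOS timings (Protocol 3.1 against 6.3.14).
2. **Data limit.** State in SAP 3.1.5.1 that the cut at last dose plus 5 days does not apply to the primary estimand. Without this, the added CDAI would be collected and then discarded.
3. **If follow-up can no longer be changed.** Say in SAP 3.3.4.1 that the estimand is treatment policy for rescue and other on-drug events, but hypothetical under MAR for discontinuations without a usable Week 12 CDAI. Define this by data availability, not by a fixed day. Add a delta-adjusted or reference-based sensitivity analysis for those subjects.

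**Cost.** Item 1 means one short visit and a longer diary for a small number of subjects (about 9-19 of 160 in the illustration). Item 2 is wording. Item 3 is wording plus a modest amount of analysis work.
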